3.6 Comparison group

(AGEK 11.3; SPIRIT #6b)

Cooling vs. Thermoneutral application

Two groups are compared to each other in order to compare the effects of cooling compared to thermoneutral application. In this way, the efficiency of cooling should be reduced to the ability to recover or performance. The cooling temperature within the cooling group will be +8 °C for both the recovery and performance tests. The temperature of the thermoneutral application will be + 32 °C for both the recovery and performance tests.

Randomization

In order to produce a high-quality study, the test subjects are each assigned to an experimental group, which are later compared with each other.

The classification is carried out randomly, and the data collected in this way are pooled accordingly according to application.

3.7 Risk/ Benefits

(ClinV, Appendix 4, 3.5; Type 25d2; ICH/EG6.2.3; AGEK 11.1; SPIRIT #Ga; MD: ISO 14155 Annex A & 150 14971)

ICH: Summary of the known and potential risks and benefits, if any, to human subjects.

For the subjects, there is a minimal risk of overload during the maximum jumping exercise for 1 min and the MVIC 60% of the ventral thigh muscles (1 min). The rehearsals are expressly informed that they have reached the maximum or submaximal load at any time. Furthermore, 2 examiners will be next to the subject during the 1 min jump load to support him/her in case of circulatory problems

SUPSI

to be able to absorb it. A fully equipped emergency kit is in the examination room at all times during the examinations. In the case of circulatory problems due to hypoglycaemia, the examination room also includes dextrose, chocolate, and ®Coca Cola Ltd. available. The test subjects are also advised to complete the test well nourished in order to minimise the risk of hypoglycaemia. A fully functional and always accessible defibrillator (Lifepak Express Defibrillator, reaplus.ch) is located in our institution. This information is communicated to the test persons (subject information).

Furthermore, any injuries to the musculoskeletal system were defined as an exclusion criterion in order not to provoke a relapse of a past injury.

More information on securing the test subjects can be found in chap. 8.1.1.

The test subject does not derive direct benefits from participating in the study.

SUPSI

3.8 Justification of the choice of population (ClinO, Art 25d4, Art. 15-17; I/IT 6.2.6; AGEK 11.2) ICH: Description of the population to be studied.

This series of studies will be conducted with healthy young volunteers. The risk of injury is considered low in this test subject population.

Inclusion Criteria

- Young healthy adults aged 18 - 30 years
- No surgical interventions on the musculoskeletal system in the trunk area and lower extremities
- Injuries to the trunk and/or lower extremities that occurred more than 1 year ago and no longer cause symptoms
- Anti-conception drugs

Exclusion criteria

- Current injuries of any kind affecting the trunk and/or lower extremities
- Injuries to the torso and/or lower extremities that occurred less than 1 year ago
- Injuries to the trunk and/or lower extremities that occurred more than 1 year ago and are still causing symptoms.
- Fear of cooling intervention
- Taking medication of any kind (even self-purchased)
- Pacemakers & cardiac arrhythmias
- Known circulatory problems Pregnancy
- Diagnosed skeletal static deviations
- Appendectomy less than 2 years ago
- Raynaud's syndrome

The subjects will be comprehensively informed about the process and possible risks before they are confirmed to participate in the study. You will also receive the information in written form and have the opportunity to ask questions. The declaration of consent explains to them what their rights and obligations are when participating. In addition, they are informed that they may withdraw from participation at any time without giving reasons, without incurring any disadvantages as a result.

SUPSI

4 STUDY OBJECTIVES

(ICH/E6 6.3; AGEK 3; SPIRIT #7)

ICH: A detailed description of the objectives and the purpose of the trial.

4.1 General objectives

In this study, the effect of a 20-minute cooling application (+8 °C) on the subjective muscle soreness and general fatigue data, as well as the objectively measurable MVIC of the ventral thigh muscles and the maximum vertical jump height after exhausting physical exertion will be investigated. The effects of the cooling application are compared with a thermoneutral application (+32 °C) and compared directly, 24 hours, 48 hours and 72 hours after the interventions. The aim is to substantiate the state of scientific knowledge and to provide therapists and physicians with further insights. This study can benefit all those who work with amateur and elite athletes.

4.2 Primary objectives

Post-Activity Cooling - Subproject A

In this subproject, the effect of post-activity cooling on objective and subjective recovery parameters is measured and compared to thermoneutral post-activity application.

Objective recovery parameters:

Maximum vertical jump height (cm)

Subjective recovery parameters:

Muscle soreness in the legs (VAS) General fatigue

data (BORG)

Preactivity Cooling - Subproject B

In this subproject, the Effect the Pre-activity cooling measured on objective and subjective performance parameters and compared with the thermoneutral preactivity application.

Objective Performance Parameters:

Maximum Arbitrary Isometric Muscle contraction (MVIC) the ventral
thigh muscles (mV)

Subjective performance parameters: Muscle

soreness in the legs (VAS)

Information on general exhaustion (BORG)

SUPSI

4.3 Secondary Objectives

None

4.4 Other safety aspects (long-term)

No short-term risks are to be expected from this study other than those discussed so far.

SUPSI

5 STUDIES OUTCOMES

(I/E6 6.4.1; AGEK 4.1; SPIRIT #12)

ICH: A specific statement of the primary endpoints and the secondary endpoints, if any, to be measured during the trial.

5.1 Primary outcomes

Muscle activity (EMG)

Increased activation of a muscle can be measured in a larger amplitude of the EMG signal. For this purpose, the absolute amplitude [mV] and the Integral over a certain time interval [mVs] are used in this study.

MVIC is measured on the Cor 1 - ergometer chair [Nm] in 90° knee flexion. The measurement moments take place directly, 24 hours, 48 hours and 72 hours after the intervention.

Jump height measurement

The jump height after the load is determined with a jump height measuring plate designed for this purpose (Just Jump Plate, Probotics Inc., Huntsville, USA). The test subjects assume a standing position on the plate. The test subjects are allowed to start from the squatting position (countermovement jump) to measure the jump height. The arms must be placed at the hips during the entire movement. The measurement moments take place directly, 24 hours, 48 hours and 72 hours after the intervention.

Subjective muscle soreness

The subjects reported their subjective feeling of muscle soreness on a visual analogue scale (VAS). The scale will be scaled from "0" (no muscle soreness present) to "10" (largest imaginable muscle soreness) in cm increments. The measurement moments take place directly, 24 hours, 48 hours and 72 hours after the intervention.

Subjective information on general exhaustion

The subjects indicate their subjective general feeling of exhaustion on a visual analogue scale (VAS). The scale is from "0" (no general exhaustion present) to "10" (greatest conceivable general exhaustion) can be scaled in cm steps. The measurement moments take place directly, 24 hours, 48 hours and 72 hours after the intervention.

5.2 Secondary outcomes

None available

SUPSI

5.3 Safety Aspects

No further outcomes are included that serve safety.

Stopping the experiment is up to the testers' assessment of the subject's resilience. If this is estimated to be too low, the examiner can discontinue the experiment.

If, according to his or her own subjective assessment, the subject does not feel well, he or she can discontinue the experiment and withdraw his or her participation in the study. There are no disadvantages for him as a result.

SUPSI

6 DESIGN STUDIES

(I/EG6.4; AGEK 4; SPIRIT #8)

6.1 Study design and justification

Randomized, controlled, double-blind study

It is an observational study of Cat. A (ClinO, Art. 20), whereby a tested medical device is tested on young, healthy volunteers during the intervention.

The group size of the participants is 40 people each (sub-protocols A & B) and 20 respectively people (subproject A) and 20 people (subproject B).

The group classification of the test setup to be tested (cooling vs. thermoneutral application) will be randomized.

Blinding of the participants is ensured by the use of a thermoneutral application. The examiners are blinded by the addition of another examiner who operates the apparatus. The responsible statistician is blinded and has no access to the personal data of the test persons and is not present when the data is collected.

6.2 Method for minimizing influence

(ICH/EG6.4.3; AGEK 4.3; SPIRIT #16, 17)

ICH: A description of the measures taken to minimize/avoid bias, including: Randomization, Blinding.

6.2.1 Randomization

The allocation to the various groups and persons of the sub-protocols takes place randomly with the drawing of a lot.

6.2.2 Blinding

Blinding of the participants is prevented by the use of a thermoneutral application warranted. The examiners are blinded by the addition of another examiner who operates the apparatus. The responsible statistician is blinded and has no access to the personal data of the test persons and is not present when the data is collected.

6.2.3 Other Methods

No other methods are used.

6.3 Code break procedure (ICH/EG6.4.8; AGEK 4.2; SPIRIT

#17b)

ICH: Maintenance of trial treatment randomization codes and procedures for breaking codes.

There is no provision for the statistician to be blinded.

SUPSI

7 POPULATION STUDIES

7.1 Inclusion Criteria

Inclusion Criteria

- Young healthy adults aged 18 - 30 years
- No surgical interventions on the musculoskeletal system in the Torso area and the lower extremities
- Injuries to the trunk and/or lower extremities that occurred more than 1 year ago and no longer cause symptoms
- Anti-conception drugs

Exclusion criteria

- Current injuries of any kind affecting the trunk and/or lower extremities
- Injuries to the torso and/or lower extremities that occurred less than 1 year ago
- Injuries to the trunk and/or lower extremities that occurred more than 1 year ago and are still causing symptoms.
- Fear of cooling intervention Taking medication of any kind Type (also self-bought)
- Pacemakers & cardiac arrhythmias
- Known circulatory problems
- Pregnancy
- Diagnosed skeletal static deviations
- Appendectomy less than 2 years ago
- Raynaud's syndrome

7.2 Recruitment and screening

(ClinO, Art 25, Appendix 3, 1.4 & 1.6; AGEK 5.1; SPIRIT #15)

Recruitment

It is advertised on the website (homepage & Facebook) of Thim van der Iaan University College Physiotherapy. The exact texts have been prepared according to the checklist of the Cantonal Ethics Commission Zurich.

SUPSI

As an advertisement (text visible):

- Homepage of the Thim van der Laan Physio School: www.Physio school.Ch
- Facebook page of the Thim van der Laan Physiotherapy School: <https://www.facebook.com/physioschule>

Screening

At the first contact, the pot. Participant informs about the course and risks of the study, as well as the conditions for and the amount of compensation. A checklist for contacting them by telephone serves as a basis.

During the first telephone contact, a questionnaire is filled out by the study management to determine the suitability as a study participant.

Advertisements, questionnaires and checklists for the first contact can be found in the supplement.

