8.6 Preventive measurements

(I/IT 6.6.2; AGEK 9; SPIRIT #11d)

ICH: Medication(s)/treatment(s) permitted (including rescue medication) and not permitted before and/or during the trial.

The questionnaire asks about the intake of medication and excludes pregnancy. If static deviations are visible but not medically diagnosed, the study leader reserves the right to measure them (leg length difference, scoliosis angle) and thus exclude a test subject from participation.

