9.1 Schedules of the various protocols

1. *Subject Information & Informed Consent*

10 Min

2. *Preparation of the subject*

15 min

3. *Running the Test Log (Sublogs)*

Partial Protocol A: first measurement + intervention - approx. 60 min	
Cooling vs. Thermoneutral application on recovery	
Cooling panel	Thermoneutral Application Group
1. 3 x Vertical Leaps VAS & BARROW (max 5 min)	1. 3 x Vertical Jumps, VAS & BARROW (max 5 min)
Max 1 min break	Max 1 min break
2. 1 minute max vertical Leaps, VAS & BARROW (1 min)	2. 1 minute max vertical jumps, VAS & BARROW (1 min)
Max 5 min break	Max 5 min break
3. Cooling (20 min)	3. Thermoneutral application (20 min)
Max 1 min break	Max 1 min break
4. 3 x Vertical Leaps, VAS & BARROW (max 5 min)	4. 3 x Vertical Jumps VAS & BARROW (max 5 min)
Directly after the Intervention	immediately after the intervention
5. 3 x Vertical Leaps, VAS & BARROW (max 5 min)	5. 3 x Vertical Jumps, VAS & BARROW (max 5 min)
24 hours after the intervention	24 hours after the intervention
6. 3 x Vertical Jumps, VAS & BARROW (max 5 min)	6. 3 x Vertical Jumps, VAS & BARROW (max 5 min)
48 hours after the intervention	48 hours after the intervention
7. 3 x Vertical Leaps, VAS & BARROW (max 5 min)	7. 3 x Vertical jumps, VAS & BARROW (max 5 min)
72 hours after the intervention	72 hours after the intervention

SUPSI

Partial Protocol B: first measurement + intervention - approx. 60 min	
Cooling vs. Thermoneutral application on performance	
Cooling panel	Thermoneutral Application Group
1. 1 x MVIC, VAS & BORG (max 3 min) Max 1 min break	1. 1 x MVIC, VAS & BORG (max 3 min) Max 1 min break
2. Cooling (20 min) Max 1 min break	2. Thermoneutral application (20 min) Max 1 min break
3. 60 % MVIC for 1 min (2 min) Max 5 min break	3. 60 % MVIC for 1 min (2 min) Max 5 min break
4. 1 x MVIC, VAS & BORG (max 5 min) immediately after the intervention	4. 1 x MVIC, VAS & BORG (max 5 min) immediately after the intervention
5. 1 x MVIC, VAS & BORG (max 5 min) 24 hours after the intervention	5. 1 x MVIC, VAS & BORG (max 5 min) 24 hours after the intervention
6. 1 x MVIC, VAS & BORG (max 5 min) 48 hours after the intervention	6. 1 x MVIC, VAS & BORG (max 5 min) 48 hours after the intervention
7. 1 x MVIC, VAS & BORG (max 5 min) 72 hours after the intervention	7. 1 x MVIC, VAS & BORG (max 5 min) 72 hours after the intervention

Sub-protocol	Total time commitment	Visits
A	Approx. 80 min	Once 60 min and 3 times for max 5 min

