9.3.2 Multiple visits

(e.g. Visit 1, Baseline (Day e.g., 1): List all exams/tests, actions to be performed according to flow chart (9.1) including also e.g., Dispense of trial medication, Scheduling of next visit)

The sub-protocols A and B are multiple visits with a duration of about 80 minutes each, which takes place as follows:

1. Subject Information & Informed Consent

The subjects will be comprehensively informed about the process and possible risks before they are confirmed to participate in the study. You will also receive the information in written form and have the opportunity to ask questions. The declaration of consent explains to them what their rights and obligations are when participating and that they may withdraw from participation at any time without giving reasons, without incurring any disadvantages as a result. More detailed information can be found in Chapter 2.7.

2. Preparing the subject

If the subject is willing to participate, he or she is instructed to change in a separate room:

- Subproject A

this sub-project does not require any further preparations.

- Subproject B

First, the areas for the placement of the electrodes are marked with a skin-friendly pen (eyeliner) and, if necessary, individual areas of the EMG electrode placements are shaved (both were explained to the test subject beforehand according to a checklist). Then the electrodes are attached.

3. Measurements

The tests are carried out in the same way as in the corresponding sub-protocol and the data is collected.

4. Indemnification and Conclusion

After completion of the individual measurement, the test subject is asked to change again in a separate room. Afterwards, they are asked how they are feeling. The subject is asked to report back to the laboratory at intervals of 24 hours (up to a maximum of 72 hours) to carry out the follow-up measurement. After completion of the measurements, the test subject will be happy to receive the compensation to which he/she is entitled. Information in the advertisement:

Flat rate Str. 200 .- after completion of the 72-hour measurement.

SUPSI

Subproject A

In subproject A, the subjects return to the laboratory 24 hours, 48 hours and 72 hours after the intervention. Here, the maximum jump height during 3 attempts is determined again. Furthermore, the subjective muscle soreness and general states of exhaustion are recorded.

Subproject B

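### Leg soreness is a primary outcome, but no entry criterion covers soreness or hard leg exercise before visit 1, no test-day reconfirmation is described, and the pre-load soreness score is left out of the model

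*Combined protocol and SAP*

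**What the plan says.** Leg soreness on a 0 to 10 VAS is a primary outcome in subprojects A and B (synopsis; 4.2; 5.1). The hypotheses in 11.1 concern the reported level over 72 h, not the change from a pre-load value.

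**Screening.** Section 7.2: "During the first telephone contact, a questionnaire is filled out by the study management to determine the suitability as a study participant". No maximum interval between the call and visit 1 is given. Section 8.6 adds: "The questionnaire asks about the intake of medication and excludes pregnancy".

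**Criteria.** The lists in the synopsis, 3.8 and 7.1 cover injuries, medication, pregnancy and several medical conditions. The item nearest to sore legs is "Current injuries of any kind affecting the trunk and/or lower extremities". None names muscle soreness or recent exercise. The only advice on behaviour before the test concerns nutrition (3.7).

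**Visit 1.** Section 9.3.2 lists information and consent, preparation, measurements and conclusion. Participants are asked how they feel only after the measurements.

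**Soreness on arrival.** It is measured. The first step in subproject A is "1. 3 x Vertical Leaps VAS & BARROW (max 5 min", where the last scale is evidently Borg, garbled in translation. In subproject B it is "1. 1 x MVIC, VAS & BORG (max 3 min) Max 1 min break". Both steps precede the load and the application.

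**Analysis.** The model in 11.4.2 has two factors, intervention and time, with time at 0, 24, 48 and 72 h. The synopsis places the first time point immediately after cooling, so the step-1 score is not a level of the model. It is not named as a covariate either.

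**The concern.** Someone who trained hard shortly before visit 1 meets every listed criterion. Their soreness is then part of the analysed ratings, and it may be changing during the same 72 h in which response to the load and the application is judged. Sore legs may also lower jump height and MVIC.

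At stake is precision. The synopsis limits the trial to 40 participants for financial reasons, so avoidable variance cannot be offset by recruiting more. In arms of about 10, a few sore arrivals can also fall unevenly.

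There is a smaller safety point. Injury, medication and pregnancy status can change between call and visit, and the visible text describes no test-day re-check.

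**Working it through.** The plan gives no SD, effect size or power, so there is no figure of its own to reproduce. The arithmetic below only shows scale.

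**Inputs from the documents.** There are 20 subjects per subproject (11.2), which is 10 per arm if allocation is 1:1. Alpha is 0.05 (11.4.2), with sidedness not stated; two-sided is used here. Sections 6.1 and 10.3 describe group size differently, so 20 per arm is also shown.

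**Assumptions.** Soreness SD from the trial load is 1.5 cm (variance 2.25). A share p of 10 to 30% arrives with r = 2 to 4 cm, fading linearly to 0 by 72 h. Carried-over soreness m is then r at time 0, 2r/3 at 24 h and r/2 for the four-visit mean. It is additive and independent of the response to the load. Arms are compared at a single time point by a t-test, which simplifies the planned repeated-measures model.

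**Added variance** = p(1 − p)m², relative to 2.25.

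| | p = 0.1, r = 2 | p = 0.2, r = 3 | p = 0.3, r = 4 |
|---|---|---|---|
| time 0 | 16% | 64% | 149% |
| 24 h | 7% | 28% | 66% |
| four-visit mean | 4% | 16% | 37% |

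**Power at 24 h, middle case, difference 1.5 cm.**
- m = 2 cm, so the added variance is 0.2 × 0.8 × 4 = 0.64.
- The SD becomes √(2.25 + 0.64) = 1.70.
- Noncentrality is 1.5 / (SD × √(2/n)). At n = 10 per arm it is 2.24 without and 1.97 with carry-over, and power falls from 56% to 46%.
- At n = 20 per arm it is 3.16 and 2.79, and power falls from 87% to 78%.

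**Chance imbalance.** Suppose 4 of 20 arrive sore and 10 go to each arm. P(2 versus 2) = C(10,2)² / C(20,4) = 2025/4845 = 0.418, so the arms differ by at least 2 sore people in 58% of allocations. A 3–1 split has probability 2 × 1200/4845 = 50%, and a 4–0 split 2 × 210/4845 = 9%. At 24 h a 3–1 split shifts the mean difference by 2 × 2 cm / 10 = 0.4 cm.

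**Use of the step-1 VAS.** Under linear fading, carry-over at 24 h is exactly 2/3 of the step-1 score. In a simulation of the middle case at 10 per arm, power was 47% unadjusted and 54% with the step-1 score as covariate, against 56% with no carry-over. The unadjusted type I error stayed at about 5%.

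**Other assumptions.** Let 10 to 40% arrive with mean m = 2 or 3 points (SD 1) that does not fade, with load SD 1.5 to 2.0. Added variance is p(1 + m²) − (pm)². Total variance rises by a factor between 1 + 0.46/4 = 1.11 (rounded down) and 1 + 2.56/2.25 = 2.14. For an effect with 80% power at 10 per arm (standardised difference 1.32), power falls to between 76% and 48%.

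**The case against.** Several stronger readings are tempting, and the documents do not support them.

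- **Suitability is closed at the call.** Section 8.6 says: "If static deviations are visible but not medically diagnosed, the study leader reserves the right to measure them", which needs the person to be seen. Section 9.3.2 places information before participation is confirmed. The questionnaires and checklists are listed in the appendix but not shown, and they may ask about exercise or be completed on the day. What stands is that the visible procedure describes no reconfirmation.
- **Nothing captures soreness on arrival.** Step 1 does, in both subprojects. The gap is that the score is not used.
- **The comparison is biased.** Allocation is random, so the expected effect is noise and chance imbalance, and the simulated type I error is nominal.
- **Baseline adjustment cannot help.** If soreness fades steadily, it recovers most of the loss. A single score cannot show whether soreness is rising or falling, so recovery could be poorer in other patterns, but that is not quantified here.
- **Newly injured or medicated people would be tested.** The documents do not show that staff would miss them. Section 5.3 says: "Stopping the experiment is up to the testers' assessment of the subject's resilience", and participants may stop at any time. These are discretionary stops, not a confirmation of eligibility, but they limit the safety point to the absence of a described re-check.

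The statement that in subproject A "this sub-project does not require any further preparations" is no evidence on eligibility. It contrasts A with electrode placement in B.

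It is also fair to object that every numerical input above is assumed and that the largest figures come from the extreme corner. The direction of the effect does not depend on them; its size does.

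**Conclusion.** The point holds in limited form. Followed as written, the plan accepts participants whose legs are already sore and analyses their ratings without the score that would identify them. The consequence is lost precision and possible chance imbalance in soreness, and possibly in jump height and MVIC.

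The true size is unknown. In the middle assumed case the loss is about 10 percentage points of power at 24 h, with 10 or with 20 per arm. It would be smaller if few arrive sore or if the step-1 score is adjusted for. This does not invalidate the trial, but the remedy is cheap and the sample size is fixed, so the change should be made before enrolment starts.

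**What to change.** 1. **7.2 and 9.3.2:** repeat and document the existing exclusion questions at visit 1, after consent and before the lot is drawn, and so before any application or load. Section 7.3 does not say when the lot is drawn, so state this as well. The order matters because anyone who leaves after allocation is dropped from the analysis (11.5), and 7.4 and 11.4.1 disagree on whether they are replaced.
2. **3.8 and 7.1:** add an entry condition of no recent strenuous leg exercise and no relevant leg soreness at step 1. The documents give no basis for a particular rest period or VAS limit, so the investigators should set both. Announce the condition in the telephone call, and rebook anyone who does not meet it before the lot is drawn.
3. **11.4.2:** name the step-1 VAS as a baseline covariate for soreness, to cover sore participants who still enter.

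The cost is protocol wording, a few minutes at visit 1, one degree of freedom in the model and some rebooked first visits. No extra participants, staff or equipment are needed. If the appendix forms already contain these checks, a cross-reference in 7.2 and 9.3.2 would settle that part.
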